12.5.4 Vector Shedding

Plasma, saliva, urine, stool, and semen (for males only) samples will be taken for PCR of vg (three times within 7-10 days after FLT201 infusion then at separate visits [at least 1 week apart] until negative vector shedding results are obtained in that matrix at three consecutive visits after Week 1). Collection of a particular matrix sample, e.g., plasma, can be stopped once negative results have been reported in that matrix at three consecutive visits at least 1 week apart after Week 1. Collection of the remaining matrices should continue until each delivers negative results at three consecutive visits at least 1 week apart after Week 1.

Samples will be analysed at a central laboratory (refer to laboratory manual for details of sample collection and processing).

12.5.5 Health-related Quality of Life

HRQoL will be evaluated using the SF-36 questionnaire.

12.5.6 Other Assessments

Pain and Fatigue Assessment

Participants will answer questionnaires relating to pain (BPI-SF) and fatigue (FACIT-Fatigue) using an electronic diary.

GD-DS3

An integrated assessment of Gaucher disease type 1 burden based on bone, hematologic and visceral domains will be performed using the Gaucher Disease Type 1 Severity Scoring System (GD-DS3).

Research Plasma

Plasma samples will be taken for research purposes. Research samples will be retained beyond the end of the study and may be analysed alongside samples taken as part of the long-term follow-up study as part of future research which has been ethically approved.

The samples will be analysed at a central laboratory.

12.6 Volume of Blood to be Drawn from Each Participant

During this study, it is expected that approximately 900 mL of blood will be drawn from each participant for central laboratory assessments.

The protocol allows for monitoring of certain parameters through local laboratories. Blood volume requirements are likely to vary between study sites; however, it is estimated that approximately an additional 500 mL will be drawn from each participant for local laboratory assessments over the course of the study.

Note: The amount of blood to be drawn for each assessment is an approximation. The amount of blood to be drawn may vary according to the instructions provided by the manufacturer or laboratory for an individual assessment.

12.7 Study Withdrawal

Participants are free to withdraw from the study, at any time, without prejudice to their continued care. The reason for discontinuation/withdrawal must be determined by the investigator and recorded in the participant's medical record and in the eCRF. If a participant is withdrawn for more than one reason, each reason should be documented in the source document and the most clinically relevant reason should be entered in the eCRF.

Reasons for withdrawal include but are not limited to:

- Protocol violation
- Withdrawal by participant
- Death
- Lost to follow-up
- Other (If "other" is selected, the investigator must specify the reason on the eCRF).

If a participant expresses their wish to withdraw from the study, the investigator should explain the importance of remaining on study follow-up, or failing this, of allowing routine follow-up data to be used for study purposes.

In the event of early withdrawal/discontinuation, every effort should be made to collect data in line with Week 38/EOS assessments.

If a participant relocates from the area, every effort should be made for the participant to be followed up at another participating study site and for this new site to take over the responsibility for the participant, or for follow-up via the participant's general practitioner.

The investigator should contact the Sponsor to discuss the withdrawal of any participant.

12.8 Definition of End of Study

The end of the study will be defined as the last visit by the last participant. All participants will be followed up for at least 5 years in a separate long-term follow-up study.

13 Dose Progression, Dose Escalation, and Temporary Halt Rules

The Sponsor will retain final responsibility for decision making on all aspects of dose progression, dose escalation, temporary halt, and stopping rules. Progression of dosing within a cohort, dose escalation/reduction, communication between active sites and the Sponsor, and temporary halt and stopping rules are detailed below and in study specific plans. The following elements will be included.

13.1 Oversight Committees

13.1.1 Independent Data Monitoring Committee

The role of the DMC is to provide independent advice on data and safety aspects of the study. The DMC will review participant data prior to a dose escalation decision, dose expansion or in the case of arising safety concerns. The DMC will be governed by a charter that dictates constitution and decision making on dose escalation/study modification and study temporary halt and stopping rules.

13.2 Dose-limiting Toxicity

A Dose-limiting Toxicity (DLT) is defined as any severe AE at least possibly related to FLT201 except for increases in ALT or AST that are not associated with increases in bilirubin. Transaminase increases should be investigated to exclude other causes but it is expected that such transaminase increases will be cases of vector-associated transaminitis which is an event anticipated with liver directed AAV gene therapy (see Section 6.5.3.1). In the case of vector-associated transaminitis, where ALT or AST levels are classed as severe, changes to the prophylactic immunosuppressive regimen will be considered for ongoing participants and before treating further participants.

The study may be stopped before completion at any time on the recommendation of the DMC or decision by the Sponsor.

13.3 Dose Escalation

13.3.1 Dose Cohorts and Dose Interval Between Participants

The planned dose escalation scheme is as follows (if subject weight is >90 kg, the dose will be calculated based on 90 kg weight):

- Cohort 1: 4.5×10^{11} vg/kg of body weight.
- Cohort 2: 1.3×10^{12} vg/kg.
- Cohort 3: 3.9×10^{12} vg/kg.
- Cohort 4: 1.1×10^{13} vg/kg.

The dose level to be tested in each cohort after Cohort 1 may be an intermediate dose between the current dose and that of the next planned dose cohort based on emerging data but would not be greater than the next planned dose. In addition, based on emerging data, including safety/tolerability, PK, PD, and clinical data, all dose cohorts may not be tested, an additional dose cohort may be added and/or a dose cohort may be further expanded beyond 3 participants. If an additional dose cohort is added the dose will not exceed 1.5×10^{13} vg/kg, which is below the NOAEL (2.57×10^{13} vg/kg).

The dose to be given is made in line with the escalation/decision rules defined in Sections 13.3.1.1, 13.3.1.2, 13.3.1.3. In all cases, safety will be assessed first followed by evaluation of efficacy.

A minimum of 4 weeks of safety/tolerability (including DLT), PK, PD, and clinical data will be assessed before dosing each participant (both within a dose cohort and before escalating to the next dose level).

All cohorts will contain at least two participants (except as described in Section 13.3.1.2). Depending on assessment of safety/tolerability (including DLT), PK, PD, and clinical data, additional participants may be treated.

Dose escalation decisions will be overseen by a DMC and will be made in accordance with the following specific rules:

13.3.1.1 Safety Assessment Based on DLT

- If 1 participant experiences a DLT, that cohort will be expanded to 3 participants
- If 2 out of 3 participants in the same cohort experiences a DLT, the DMC will be convened to consider a dose reduction. The DLT rate is expected to be less than or equal 33%.

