25. Any clinical condition (medical or psychiatric) that, in the opinion of the investigator, could jeopardise safety or compromise ability of the participant to participate in this study.

Methodology:

This is a phase 1/2, open-label, dose escalation and expansion study of FLT201 in patients with Gaucher disease type 1. Participants who provide consent to participate in this study will be screened for eligibility over a 16-week period. On the day prior to infusion (Day -1), the participant

will attend the investigational site and final eligibility assessments will be conducted. On Day 1, FLT201 will be administered as a single dose, slow intravenous infusion into a peripheral vein, and the participant will be monitored closely for at least 8 hours following the infusion. Following satisfactory results from safety evaluations conducted on Day 1, the participant will be discharged from the investigational site. Post FLT201 dosing, all participants will enter a 38-week post-infusion follow-up period during which safety and efficacy assessments will be performed. On completion of the 38-week follow-up period, all participants will be followed under a separate long-term follow-up protocol that will assess safety and efficacy for at least a total of 5 years post-dosing.

Study Schema:

The study will be conducted in 2 parts:

Part 1: Dose Escalation in Previously Treated Patients

Approximately 4 dose cohorts (12 participants) are planned to be tested in a dose escalation scheme in previously treated patients. Each dose cohort is planned to include at least 2 participants (except if GCase activity in the first participant in the cohort is below the normal range [e.g., $<1.5 \mu\text{mol/L/h}$, though this value will vary depending on the specific laboratory] and no DLT observed; see below). A third participant may be added, depending on safety/tolerability (including DLT) observed following treatment. Safety, PK, PD and clinical data will be evaluated at pre-defined timepoints.

The planned dose escalation scheme is as follows (if subject weight is $>90 \text{ kg}$, the dose will be calculated based on 90 kg weight):

- Cohort 1: 4.5×10^{11} vector genomes (vg)/kg of body weight
- Cohort 2: 1.3×10^{12} vg/kg
- Cohort 3: 3.9×10^{12} vg/kg
- Cohort 4: 1.1×10^{13} vg/kg

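### Two DLTs in a cohort's first two participants do not literally meet the DLT review trigger, while the expansion rule still calls for a third; the two rules need reconciling with the permitted cohort sizes

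*Protocol*

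**What the plan says.** Protocol 13.3.1.1, repeated in the synopsis under the dose escalation and cohort expansion rules, gives two DLT rules:

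- Expansion: "If 1 participant experiences a DLT, that cohort will be expanded to 3 participants".
- Review: "If 2 out of 3 participants in the same cohort experiences a DLT, the DMC will be convened to consider a dose reduction".

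It adds that "The DLT rate is expected to be less than or equal 33" per cent, without a derivation. Section 13.3.1 presents these as specific rules that escalation decisions are to follow.

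On cohort size, 13.3.1 says: "All cohorts will contain at least two participants (except as described in Section 13.3.1.2)". That exception (13.3.1.2) covers a first participant with low GCase activity and no DLT. Section 13.3.1 also says that, depending on emerging data, "a dose cohort may be further expanded beyond 3 participants".

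On the third participant, the synopsis (study schema, Part 1) is permissive: "A third participant may be added, depending on safety/tolerability (including DLT) observed following treatment". Section 8.1 is permissive in the same way. The synopsis statistical methods and SAP 4.2 describe expansion after a DLT as an option.

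The general controls are:

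- 13.3.1: "A minimum of 4 weeks of safety/tolerability (including DLT), PK, PD, and clinical data will be assessed before dosing each participant".
- 13.1.1: "The DMC will review participant data prior to a dose escalation decision, dose expansion or in the case of arising safety concerns".
- 13.7 refers to DMC recommendations on within-cohort decisions as well as on escalation.
- 13.2 allows the study to be stopped at any time.
- 13.6 holds enrolment for listed events, including an FLT201-related severe AE that is life-threatening or needs urgent intervention.

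SAP 3.3.1 refers back to the protocol for escalation and adds no DLT count.

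**The concern.** The review trigger names one configuration only, two DLTs among three participants. Dosing is sequential, so a cohort can reach two DLTs before a third participant has been treated. At that point the first DLT has already activated the expansion rule, the second does not cancel it, and the review rule has not been met on its wording. A site or sponsor team following 13.3.1.1 literally is told to complete the cohort at a dose where every treated participant has had a DLT. Someone following the study schema or 8.1 would regard the third participant as optional.

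This is a first-in-human escalation, and 13.3.1.1 holds the only DLT counts in the plan. What is at stake is whether DMC consideration of a dose reduction is required by rule before a third dosing, or depends on the more general provisions.

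**Working it through.** **Inputs.** The two DLT rules and the expected rate of at most 33% come from Protocol 13.3.1.1. The minimum cohort size, sequential dosing and possible expansion above three come from 13.3.1. The documents give no true DLT rate *p*, so it is an assumption shown over a range. Participants are taken as independent with the same *p*.

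**1. The plan's own figure.** The 33% is an expectation with no calculation behind it, so there is nothing to reproduce. It is consistent with the trigger: 1/3 = 33.3% is the highest result in a cohort of three that stays below 2 out of 3.

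**2. The rules applied in sequence.**

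| State of cohort | Expansion rule | Review rule, read literally |
|---|---|---|
| 1 DLT in 1 | expand to 3 | not met |
| 2 DLTs in 2 | still in force | not met |
| 2 DLTs in 3 | complete | met |

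In this sequence the DMC review that precedes an expansion can fall after the first DLT and before the second is known. No text requires another expansion review after the second. If instead the first participant has no DLT and the second does, expansion and its review both follow the second result, and the problem does not arise.

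**3. What a third result could add.** After two DLTs the cohort ends at (2 + 0)/3 = 66.7% or (2 + 1)/3 = 100%. Neither is below 2 out of 3, so the third result cannot change whether review is warranted.

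**4. How often the state arises.**

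- P(2 DLTs in the first 2) = p²
- P(at least 2 DLTs in 3) = 3p²(1 − p) + p³
- Share of the latter already at 2 of 2 before the third dose = p² / [3p²(1 − p) + p³] = 1/(3 − 2p)

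| Assumed p | 2 of 2 | At least 2 of 3 | Share already at 2 of 2 |
|---|---|---|---|
| 10% | 1.0% | 2.8% | 35.7% |
| 20% | 4.0% | 10.4% | 38.5% |
| 25% | 6.25% | 15.6% | 40.0% |
| 1/3 | 11.1% | 25.9% | 42.9% |
| 50% | 25.0% | 50.0% | 50.0% |

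Worked at p = 1/3: (1/3)² = 0.111; 3 × 0.1111 × 0.6667 + 0.0370 = 0.259; 0.1111/0.2593 = 0.429.

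**5. Cohorts above three.** In a cohort of four, the trigger read as a count of two is met at 2/4 = 50%. Read as a proportion of two thirds it needs 2/3 × 4 = 2.67, that is, three DLTs. The text does not choose between these readings.

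**The case against.** The strongest reply is that several controls stand between a second DLT and a third dosing. At least four weeks of data, expressly including DLTs, must be assessed before each participant. The DMC acts on safety concerns and advises within cohorts. The study can be stopped at any time, and the more serious events trigger the halt in 13.6. This stands. A reader might infer from 13.3.1.1 that a third participant would be dosed without review, or that only the general safety-concern clause remains. The documents do not support either inference.

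A reader might also think that a cohort of one has no DLT safeguard. That is not supported either, since 13.3.1.2 allows escalation after one participant only when no DLT was seen.

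A sensible reading narrows the gap further. Once the first DLT sets the cohort at three, a second guarantees at least two of three, so the trigger could be treated as met. That is reasonable, but the text does not say it.

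It is also fair that the trigger only convenes the DMC to consider a reduction and is not a stopping rule, and that the DMC charter and study-specific plans, which are not among the documents, may cover the case.

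What the reply does not remove is the conflict in the protocol's own wording. None of the general controls states a DLT count for two of two. The severe-AE criterion in 13.6 is narrower than the DLT definition in 13.2, so a DLT can fall outside the halt.

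**Conclusion.** The point holds as a defect in the specific DLT rule and should be corrected. It is not a finding that oversight is missing. Followed literally, 13.3.1.1 and the synopsis rules keep the expansion instruction alive after two DLTs in two participants and leave the review trigger unmet. They also disagree with the synopsis study schema and 8.1 on whether a third participant is mandatory, and they give no meaning to the trigger above three.

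Within the protocol's expected range, the chance per cohort of two DLTs in the first two runs from 1% at a true rate of 10% to 11% at one third. It is 25% at 50%, which is above that range. These figures rest on an assumed common rate and independence between participants. A reader might take them as the chance that a third participant is exposed. They are not, because that would also require the four-week data assessment, the DMC and the sponsor all to let dosing proceed.

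**What to change.** In the next protocol amendment, reconcile the synopsis (study schema and escalation rules), 8.1, 13.3.1 and 13.3.1.1 on two matters:

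- Make the mandatory and permissive wordings on the third participant agree.
- Define the DLT review trigger for every DLT count and cohort size the protocol permits, including two DLTs in the first two participants and cohorts above three.

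What the trigger should be, and when it applies, is for the sponsor and DMC to decide. The DMC charter should be checked so that it matches.

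The cost is a sentence or two in the protocol and a check of the charter. No change to sample size or analysis follows.

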13.3.1.2 GCase Activity Level

If GCase activity is below the normal range (e.g., $<1.5 \mu\text{mol/L/h}$ though this value will vary depending on the specific laboratory) and no DLT is observed in the first participant in the cohort then dose escalation to the next dose cohort would occur after this first participant to avoid treating the next participant with a dose predicted to be below the therapeutic range.

13.3.1.3 Safety Rules Based on NOAEL

The dose levels planned for Cohorts 1 to 4 are below the NOAEL of the FLT201 GLP toxicology study ($2.57 \times 10^{13} \text{ vg/kg}$).

If deemed necessary by the Sponsor, and in consultation with the DMC, up to 3 further participants may be enrolled in an additional cohort. The dose level for this cohort may be a previously tested dose level, intermediate dose level, or escalated based on all available safety/tolerability (including DLT), PK, PD, and clinical data when the final participant in the Cohort 4 has completed at least 4 weeks' post-dose follow-up. The highest dose that may be tested will not exceed $1.5 \times 10^{13} \text{ vg/kg}$, which is below the NOAEL ($2.57 \times 10^{13} \text{ vg/kg}$), except by protocol amendment.

13.4 Dosing Previously Untreated Patients

When the last participant in Part 1 has completed at least 12 weeks' follow-up post-FLT201 administration, a dose will be selected for Part 2 based on safety/tolerability (including DLT), PK, PD, and clinical data from participants in Part 1.

Progression from Part 1 to Part 2 will be by protocol amendment only, based on all available safety/tolerability (including DLT), PK, PD, and clinical data, evaluated in discussion with DMC.

For the dose evaluation decisions in Part 2, the total number of participants that experience DLTs in both Parts (Part 1 + Part 2) will be considered.

13.5 Temporary Halt

Once a temporary halt is applied to the study a review by the DMC will take place. If the Sponsor deems it appropriate to restart the study; this can be done only following approval by the relevant competent authorities, IECs/IRBs, and any local approvals required.

13.6 Temporary Halt Rules

Further enrolment into the study will be put on hold in the event of any of the following:

- Death of a participant related to FLT201
- Development of malignancy related to FLT201
- Development of neutralising anti-GCase antibodies, defined as a positive result from the central laboratory in conjunction with a decrease in GCase activity levels and an increase in Gaucher disease biomarkers (e.g., lyso-Gb1). *
- Severe AE with life-threatening consequences or urgent intervention indicated in a subject related to FLT201

*The investigator should contact the Medical Monitor if there is a suspicion of neutralising anti-GCase antibodies. Transient antibodies, defined as a negative GCase antibody test after a positive result, with no significant drop in plasma GCase activity level, would not trigger the temporary halt rules.

Participants who have already received the vector infusion will continue to be followed per the protocol. If, following a safety review by the independent DMC, the Sponsor deems it appropriate to restart the study; this can only be done following approval by all relevant competent authorities, IECs/IRBs and any local approvals required.

13.7 Communication Plan for Dissemination of Safety Data

The independent DMC will review participant data prior to any dose escalation decision, dose expansion or in the case of any arising safety concerns (Section 13.1.1). All recommendations will be based on a thorough risk-benefit assessment based on all available data at each review. The DMC recommendation regarding both within-cohort decisions and dose escalation decisions will be disseminated to all sites by the Sponsor.

Investigators are to immediately report AEs that meet the criteria for a temporary halt of the study (Section 13.6), Adverse Events of Special Interest (AESI) (Section 14.2.9), Serious Adverse Events (Section 14.3), or Other Important Medical Events (Section 14.3.9).

If the investigator and Sponsor agree that temporary halt criteria have **not** been met, then dosing of the study may continue as per current protocol. Discussion between the investigator and Sponsor should be documented.

In all other circumstances, the Sponsor will convene an urgent meeting (to include relevant Clinical Development and Safety representatives) to determine if temporary halt criteria have been met. If it is determined that temporary halt criteria have been met, the Sponsor will immediately contact all investigators to notify them of the temporary halt to dosing in the study, and, in addition, the relevant competent authorities and IECs/IRBs will be informed.

To re-start the study, the independent DMC must complete a benefit-risk review and be satisfied that any proposed amendments are appropriate, and such amendment must be approved by all relevant competent authorities, IECs/IRBs, and any other local approvals prior study re-start.

14 Safety Definitions, Reporting, and Follow-up

An AE is any untoward medical occurrence in a clinical investigation participant administered a pharmaceutical product. An AE can, therefore, be any unfavourable and unintended sign (including an abnormal laboratory finding), symptom, or disease temporally associated with the use of a medicinal investigational product, whether or not related to the medicinal investigational product (International Council for Harmonisation of Technical Requirements for Pharmaceuticals for Human Use Guidance E2A 1995).

14.1 Adverse Event Definitions

Adverse event (AE) definitions are provided in [Table 4](#).

Table 4: Adverse Event Definitions

Term	Definition
Adverse event	Any untoward medical occurrence in a clinical investigation participant administered a pharmaceutical product that does not necessarily have a causal relationship with the treatment
Adverse reaction	All untoward and unintended responses to an investigational medicinal product related to any dose administered
Serious adverse event	Any AE that: 
 • results in death, • is life-threatening*, • requires hospitalisation** or prolongation of existing hospitalisation, • results in persistent or significant disability or incapacity or consists of a congenital anomaly or birth defect. • is considered an important medical event (defined below)
SUSAR	A suspected unexpected Adverse Reaction which is also categorised as serious
Important medical event	These events may jeopardise the participant or may require an intervention to prevent one of the above characteristics/consequences. Such events should also be considered “serious.” See Section 14.3.8 for study-specific events that should also be considered as important medical events

Abbreviations: AE=adverse event; SUSAR=suspected unexpected serious adverse reaction.

* A life-threatening event refers to an event in which the participant was at risk of death at the time of the event; it does not refer to an event which hypothetically might have caused death if it were more severe.

** Hospitalisation is defined as an in-patient admission, regardless of length of stay. Hospitalisation for pre-existing conditions, including elective procedures do not constitute an SAE.

